### *Measurement of outcomes:*

In the cost-utility analysis, we will use Quality Adjusted Life Years (QALYs) to measure the impact of the healthcare intervention on participants' health-related QoL. QALYs provide a comprehensive and standardized metric that combines both the quantity and quality of life experienced by individuals. To calculate QALYs, we will employ the EQ-5D-5L questionnaire. Using a preference-based algorithm, we will convert EQ-5D-5L responses into a single utility index score, representing each participant's health-related quality of life.

QALYs will be calculated based on the utility index scores over the study period using Danish population norms. We will use linear interpolation between measurement points (baseline, 3 months, 6 months, and 12 months). In the cost-effectiveness analysis, iHOT-33 (0-100) total scores will be used. Outcomes will be summarized in Table 4.

*Base-case cost-effectiveness and cost-utility analysis:*

Missing data will be imputed using Multiple Imputation with Chained Equations (MICE). Cost and effect data will be assumed to be missing at random, which means that missing observations are explained by observed variables. The imputation model will include outcome variables and predictor variables that differ at baseline, are related to missing data, or are associated with the outcome. To account for the skewed distribution of cost data, predictive mean matching will be used in MICE. The number of imputed datasets will be increased until the loss of efficiency is less than 5%. Each of the imputed datasets will be analyzed separately. Results from the multiple datasets will be pooled using Rubin's rules. To account for the possible clustering of data, analyses will be performed using linear mixed-effect models. Accounting for the possible clustering of data at the hospital level is very important, as most economic evaluations fail to do so, whereas ignoring the possible clustering of data might lead to inaccurate levels of uncertainty and inaccurate point estimates.

The incremental cost-effectiveness ratio (ICER) and cost-utility ratio (ICUR) will be calculated by dividing the between-group difference in change in mean total costs by the difference in mean change for QALYs and iHOT-33 scores. The ICER and ICUR provide a measure of the additional cost per additional QALY, or iHOT-33 point gained or lost by physiotherapist-led exercise compared to usual care. The ICER and ICUR will be presented in Table 5. Bootstrapping techniques will be used to estimate the uncertainty surrounding the cost-effectiveness estimates. Cost-effectiveness planes (Figure 2) visually represent the differences in costs and health outcomes, and cost-effectiveness acceptability curves (Figure 3), graphically present the impact of uncertainty of the ICER and ICUR (the probability of the physiotherapist-led exercise intervention being cost-effective compared to usual care, with possible values of the cost-effectiveness threshold).

*Sensitivity analysis:*

Various one-way sensitivity analyses will be performed to test the robustness of the study results. First, a complete case analysis will be performed by using only cases with complete data for both outcomes and costs. 20 of the 120 patients enrolled in the study will be from Melbourne, Australia. A sensitivity analysis will be conducted, excluding the patients from Australia because of sample size disparity (100 in Denmark and 20 in Australia) and possible variations in healthcare practices, costs, and outcomes across countries.

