### **Sample size calculation**

The sample size calculation is based on a clinical superiority calculation using data from a pilot RCT by Kemp et al. Kemp et al. found a mean change of 27 (SD 26) points on the iHOT-33 in their strength exercise group (e.g., intervention group) and a mean change of 11 (SD 8) points in their stretching group (e.g., control group) after 12 weeks of intervention (between-group difference of 16 [95% CI -9; 38] points). The superiority margin is a 6 points MCID in the between-group change on the iHOT-33. The estimated mean difference of 16 points, a superiority margin of 6 points, a SD of 19.2, a power of 80% and an alpha level of 5% results in a total sample size of n=94 (n=47 in each group). After allowing a dropout-rate of up to 28% our required sample size will be n=120 (n=60 in each group).

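### The 5% efficiency rule for the number of imputations in the base-case economic analysis is loose: it tolerates Monte Carlo error of about 0.22 of the standard error

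*SAP*

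**What the plan says.** The rule stands in the SAP under the base-case cost-effectiveness and cost-utility analysis. Imputation is by chained equations: "Missing data will be imputed using Multiple Imputation with Chained Equations (MICE"). Costs get their own treatment: "To account for the skewed distribution of cost data, predictive mean matching will be used in MICE". The number of datasets is then set by a single criterion: "The number of imputed datasets will be increased until the loss of efficiency is less than 5" per cent. Each dataset is analysed separately, and "Results from the multiple datasets will be pooled using Rubin's rules".

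The pooled cost and effect differences feed the ICER, the ICUR, the cost-effectiveness planes and the acceptability curves. On uncertainty the section adds: "Bootstrapping techniques will be used to estimate the uncertainty surrounding the cost-effectiveness estimates".

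The SAP gives no minimum number of imputations, no tolerance for Monte Carlo error, no random seed, and no expected FMI for costs or EQ-5D-5L. The only figure related to missing data is the dropout allowance in the sample size section: "After allowing a dropout-rate of up to 28% our required sample size will be n=120 (n=60 in each group").

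**The concern.** Multiple imputation draws random values, so the pooled result depends partly on the seed. How much it depends on the seed is set by the number of imputations, which is entirely in the analyst's hands. A criterion of 5% lost efficiency sounds strict. On the standard-deviation scale it is not, because a 5% share of variance is a 22% share of the standard error.

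The analysis concerned is the one behind hypothesis (ii), that the exercise intervention is cost-effective at 12 months. At stake is whether a second analyst who follows the same plan on the same data would report nearly the same cost difference, QALY difference and probability of cost-effectiveness.

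**Working it through.** **Inputs.** From the SAP: loss of efficiency below 5%, and pooling by Rubin's rules. Assumed: FMI from 0.20 to 0.50. The 28% dropout allowance serves only as a stand-in within that range. The SAP's own counts, 94 needed out of 120 randomised, imply 1 − 94/120 = 21.7%, so 0.217 is shown as well. There is no stated number of imputations to reproduce.

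**Step 1: datasets at which the rule is met.** With W the within-imputation and B the between-imputation variance, take FMI = B/(W + B). Then

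loss = 1 − 1/(1 + FMI/m) < 0.05, so FMI/m < 0.05/0.95 = 0.0526, so m > 19 × FMI.

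**Step 2: Monte Carlo error there.** The Monte Carlo variance of the pooled estimate is B/m, and the total variance is W + B + B/m. Their ratio is (FMI/m)/(1 + FMI/m), which is exactly the loss of efficiency. The rule therefore caps the Monte Carlo SD at √0.05 = 0.22 of the pooled standard error at any FMI. The table gives √(FMI/m), which is the error relative to the standard error with very many imputations.

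| FMI (assumed) | 19 × FMI | smallest m | loss at that m | Monte Carlo SD / SE | same at m = 50 |
|---|---|---|---|---|---|
| 0.20 | 3.80 | 4 | 4.8% | 0.224 | 0.063 |
| 0.217 | 4.12 | 5 | 4.2% | 0.208 | 0.066 |
| 0.28 | 5.32 | 6 | 4.5% | 0.216 | 0.075 |
| 0.40 | 7.60 | 8 | 4.8% | 0.224 | 0.089 |
| 0.50 | 9.50 | 10 | 4.8% | 0.224 | 0.100 |

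A simulation of Rubin pooling (200,000 replicates, FMI 0.28, m = 6) gave 0.216, in agreement. Two runs with different seeds would differ with an SD of √2 × 0.216 = 0.31 of a standard error.

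**Step 3: loss of precision.** At FMI 0.28 and m = 6 the standard error is √(1 + 0.28/6) = 1.023 times its limiting value, so about 2.3% wider. At m = 50 it is √(1 + 0.28/50) = 1.003 times. This part of the harm is slight.

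**Step 4: effect on an acceptability probability.** This step assumes that the curve is read from the pooled estimate and standard error on a normal scale. In the same simulation, a probability of 0.80 with very many imputations came out between 0.66 and 0.90 across seeds (95% range) at m = 6, and between 0.75 and 0.84 at m = 50.

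**Step 5: stability of the stopping point.** With m = 6 and a true FMI of 0.28, the estimated FMI ran from 0.09 to 0.50 (5th to 95th percentile). A rule applied to the estimated FMI could therefore stop at quite different numbers by chance.

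**The case against.** The strongest reply is that the rule already does what is asked. A reader might infer that it leaves seed-to-seed variation in the estimate uncontrolled. That is wrong: Step 2 shows that the loss of efficiency is the Monte Carlo share of the total variance, so the rule bounds it. What stands is that the bound is loose.

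A reader might also infer that the plan will use about six datasets. The SAP does not support this. Six needs an FMI of about 0.28, and the 28% is a dropout allowance for sample size, not an FMI for costs or QALYs. Good predictors in the imputation model lower the FMI. Totals built from several questionnaires raise it: QALYs alone draw on four time points ("We will use linear interpolation between measurement points (baseline, 3 months, 6 months, and 12 months"). Nor does the rule forbid more datasets. It reads as a stopping point, though, and 4 to 10 would comply.

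The acceptability figures need care. At the steepest point of the normal curve, a shift of 0.2 SE moves 50% to about 58%. At 80% the same shift gives about 85%. The SAP does not say how bootstrapping and imputation are combined. If imputation is repeated within bootstrap samples, many more imputations enter the curve, and the figures in Step 4 do not carry over. No movement of the ICER itself has been computed, and skewness and predictive mean matching enter none of the figures.

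Finally, Table 5 lists imputed datasets as a sensitivity analysis, while the text makes imputation part of the base case. On either reading, imputed results are reported and depend on this rule.

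**Conclusion.** The point holds as a free improvement. The only rule for the number of imputations tolerates Monte Carlo error of about 0.22 of the standard error in the pooled cost and QALY differences. This follows from the 5% criterion and Rubin's formula, and does not depend on the FMI. The count of 4 to 10 datasets does depend on it: it assumes an FMI of 0.2 to 0.5, which the SAP does not give.

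A reader might infer biased results or invalid confidence intervals. The SAP does not support that. Rubin's rules add B/m to the variance, so the intervals allow for a finite number of imputations. The primary iHOT-33 analysis is untouched, because the SAP applies no imputation there. The harm is limited to avoidable seed-dependence and slight imprecision in the economic base case and what is derived from it.

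**What to change.** Replace the sentence on loss of efficiency with a fixed number of imputed datasets, for example m = 50, and a random seed set in advance. State that the Monte Carlo error of the cost difference and of each effect difference will be reported beside the pooled estimates.

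The choice of 50 can be justified by a tolerance. A Monte Carlo SD of 0.10 of the standard error needs FMI/m = 0.01, so m = 100 × FMI, which is 28 at FMI 0.28 and 50 at FMI 0.50. Fifty datasets therefore keep the error at or below 0.10 over the whole assumed range.

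The cost is computing time only. Data collection, sample size and the quantities estimated do not change.

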## **STUDY METHODS**

### **Trial design**

The Better Hip trial is a multicenter, stratified (by hospital site), randomized (allocation 1:1), controlled, parallel-group, assessor-blinded, superiority trial conducted in Denmark (Aarhus, Horsens, Hvidovre, Aalborg, and Odense) and Australia (Melbourne).

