## **Timing of outcome assessments**

Outcome assessments are planned at baseline and 6 months follow-up for performance-based physical functioning tests (e.g., maximal muscle strength in the one-repetition maximum unilateral leg press, single leg jump for distance, and one leg rise test). Outcome assessments are planned at baseline, 3, 6, and 12-month follow-ups for patient-reported outcome measures and cost. See Table 1 in the study protocol.

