## **Health Economic Evaluation**

Incremental cost-effectiveness (ICER) and cost-utility (ICUR) analyses will be conducted from both a societal and healthcare perspective to estimate the cost-effectiveness and cost-utility of supervised strength exercise compared to usual care. The time horizon will be 12 months. Costs will be expressed in Danish Crowns (DKK) (Price year 2026). The base-case cost-effectiveness analysis will follow the intention-to-treat principle. Findings will be reported following the Consolidated Health Economic Evaluation Reporting Standards (CHEERS) guideline.

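### The economic models name no baseline covariate and the QALY effect is defined in two ways, so chance imbalance in baseline EQ-5D utility is either partly left in or over-corrected, and precision is lost

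*SAP*

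**What the plan says.** All of this is in the SAP.

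- **QALY construction** (Health Economic Evaluation, Measurement of outcomes): "We will use linear interpolation between measurement points (baseline, 3 months, 6 months, and 12 months". On the horizon: "The time horizon will be 12 months".
- **Model** (base-case cost-effectiveness and cost-utility analysis): "To account for the possible clustering of data, analyses will be performed using linear mixed-effect models". Clustering by hospital is the only reason given, and no fixed effects are listed. Baseline variables are mentioned in that section only as predictors in the multiple-imputation model.
- **Effect measure.** The paragraph defining the ICER and ICUR divides by a between-group difference in the mean change of QALYs and iHOT-33. Table 4 gives QALYs a baseline and a change column. The Table 5 footnote instead defines the effect as the mean difference in the outcome between arms. A baseline QALY is defined nowhere.
- **Sensitivity analyses.** The text lists a complete-case analysis and one excluding Melbourne. Table 5 adds a row for imputed datasets. None is described as baseline-adjusted.
- **Data available** (Timing of outcome assessments): "Outcome assessments are planned at baseline, 3, 6, and 12-month follow-ups for patient-reported outcome measures and cost".

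**The concern.** Interpolation makes the QALY an area under a curve that starts at baseline utility. Baseline utility therefore enters the outcome directly, and again through its correlation with the later visits. If the arms differ at baseline by chance, part of that difference appears as a QALY difference unless the model accounts for it.

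The two effect definitions treat the imbalance differently. A plain difference leaves part of it in. The natural reading of a change, QALY minus baseline utility times one year, removes too much. An analyst could follow either and remain within the plan, and the two can give different ICURs, cost-effectiveness planes and acceptability curves. Cost-effectiveness is one of the three hypotheses in the SAP's introduction, so its estimator should be fixed in advance.

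**Working it through.** **Plan figures.** The SAP gives no size or power for the economic analysis, so there is no economic figure to reproduce. The only sample-size input used here is 60 per arm ("After allowing a dropout-rate of up to 28% our required sample size will be n=120 (n=60 in each group"). The evaluable number behind it, 47 per arm, does reproduce: a difference of 16 - 6 = 10 points and SD 19.2, with 80% power and a one-sided 5% level, give 46 per arm by the normal formula and 47 with the t distribution. That calculation has no further bearing on this point.

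**QALY weights.** The trapezoidal rule over 0, 3, 6 and 12 months, in years, gives:

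- baseline: 0.25/2 = 0.125
- 3 months: (0.25 + 0.25)/2 = 0.25
- 6 months: (0.25 + 0.5)/2 = 0.375
- 12 months: 0.5/2 = 0.25

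They sum to 1, and their squares sum to 0.28125.

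**Assumptions, not in the SAP.** Utility has the same SD at every visit. Every pair of visits has the same correlation r, taken as 0.3, 0.5 or 0.7. Where an absolute size is shown, the utility SD is 0.15 to 0.20.

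**Formulas**, in units of the utility variance, with Q the QALY and U0 baseline utility:

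- slope of Q on U0: b = 0.125 + 0.875r. This is the share of a baseline imbalance carried into the plain difference.
- share carried if baseline utility is subtracted: b - 1
- Var(Q) = r + (1 - r) × 0.28125
- Var(Q - U0) = Var(Q) - 2b + 1
- residual variance after adjustment: Var(Q) - b²
- SE cut from adjustment: 1 - sqrt(residual variance / comparator variance)

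| | r = 0.3 | r = 0.5 | r = 0.7 |
|---|---|---|---|
| Share carried, plain difference (b) | 0.39 | 0.56 | 0.74 |
| Share carried, baseline subtracted (b - 1) | -0.61 | -0.44 | -0.26 |
| Var(Q) | 0.497 | 0.641 | 0.784 |
| Var(Q - U0) | 0.722 | 0.516 | 0.309 |
| Residual variance, adjusted | 0.347 | 0.324 | 0.240 |
| SE cut against raw QALY | 16% | 29% | 45% |
| SE cut against baseline-subtracted QALY | 31% | 21% | 12% |

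Worked column, r = 0.5: b = 0.125 + 0.4375 = 0.5625; Var(Q) = 0.5 + 0.5 × 0.28125 = 0.6406; residual variance = 0.6406 - 0.3164 = 0.324. The cut against the raw QALY is 1 - sqrt(0.324/0.6406) = 0.29. Against the baseline-subtracted QALY it is 1 - sqrt(0.324/0.516) = 0.21.

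**Absolute size.** With 60 per arm, one standard error of the baseline difference is SD × sqrt(2/60) = 0.183 SD, or 0.027 at SD 0.15 and 0.037 at SD 0.20. The resulting shift in the plain QALY difference runs from 0.3875 × 0.0274 = 0.011 to 0.7375 × 0.0365 = 0.027.

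**The case against.** **A mixed model can hold covariates, and silence is not exclusion.** The SAP lists no fixed effects for this model, not even arm, and the paper it cites there has covariate adjustment in its title. That is fair: the plan does not say that covariates are excluded. But it names none, and a cited title does not pre-specify a model.

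**Baseline already enters by subtraction.** The ICER/ICUR paragraph and Table 4 speak of change. This is partly right, and it is why the point cannot rest on the plain difference alone. But no baseline QALY is defined, the Table 5 footnote says otherwise, and subtracting baseline utility imposes a slope of 1 where the calculation gives 0.39 to 0.74.

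**The consequence is efficiency, not validity.** This stands. Allocation is randomized 1:1 and stratified by site, so either estimate is unbiased on average, and the planned bootstrap already reflects chance imbalance in its uncertainty. Imputing with baseline predictors, however, fills gaps and does not adjust the comparison between arms.

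**iHOT-33 and costs differ from QALYs.** This also stands. The clinical mixed model has baseline as a time point with a group-by-time interaction. If the economic iHOT-33 estimate came from it, baseline iHOT-33 would be in the model, though not as a covariate. The SAP does not say whether it does. For costs there is nothing from which to compute a gain.

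**Conclusion.** The point holds as a gap in specification that costs precision. No baseline covariate is named in the economic models, the QALY effect has two inconsistent definitions, and neither definition removes a baseline imbalance. Under the stated assumptions, adjustment is more precise than both across the whole range of correlations examined.

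The sizes depend on the assumed SD and correlation. With equal SDs, the existence of a carried share does not depend on the SD, and its sign is the same at every correlation from 0.3 to 0.7.

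A reader might infer more than the SAP supports:

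- **That the whole imbalance passes into the QALY difference.** Only part does under the plain difference, and it enters with reversed sign under subtraction.
- **That the economic result is biased or invalid.** Randomization rules that out on average. The harm is error given the realized imbalance, and a wider interval than necessary.
- **That the shift rivals the true QALY effect.** The SAP states no expected QALY effect, so there is nothing to compare 0.011 to 0.027 with.
- **That the same gains apply to iHOT-33 and costs.** The reasoning is the same in kind, but the calculation covers QALYs only.

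**What to change.** - State that the QALY difference comes from the planned linear mixed model, keeping its site term, with arm and baseline EQ-5D utility as fixed effects.
- Use this same model in every imputed dataset and every bootstrap replicate, so that the ICUR, the cost-effectiveness plane and the acceptability curve rest on one estimator.
- In the ICER/ICUR paragraph, replace the change in QALYs with the baseline-adjusted difference in 12-month QALYs. Do the same for the QALY baseline and change columns in Table 4, and word the Table 5 footnote to match.
- By the same logic, though without a computed gain, include baseline iHOT-33 in the model for the 12-month iHOT-33 effect and, where measured, baseline cost in the cost model.

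The cost is a few sentences in the SAP, one covariate per model and an edited table shell. Baseline utility is already collected, so no new data or visits are needed. The change should be made before unblinded data are seen.

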### **Pre-specified exploratory analyses: Adherence and volume**

A pre-specified exploratory secondary analysis will investigate whether exercise session adherence (expressed as a % of supervised sessions and as a % of total prescribed sessions) and exercise volume are associated with strength exercise effectiveness on hip-related quality of life (e.g., iHOT-33, 0-100), maximal muscle strength (e.g., 1 RM unilateral leg press) and functional performance (e.g., One Leg Jump for Distance and One Leg Rise Test). Multiple linear regression will be applied in all analyses. With a rule of thumb of 10 observations (i.e., participants) per independent variable, and approximately 60 participants in the physiotherapist-led strength exercise group, we can include 6 independent variables (e.g., categories) in the regression model. The independent variables will be potential moderators measured at baseline and at 6-month follow-up that were expected to be associated with changes in the outcome (e.g., dependent variable). The dependent variable in each of the multiple linear regression models will be the change in the iHOT-33 score (0-100), maximal muscle strength (e.g., 1 RM unilateral leg press), and functional performance (e.g., One Leg Jump for Distance and One Leg Rise Test) from baseline to 6-month follow-up. The independent variables will be 1) Supervised exercise adherence (expressed as a % of maximal 12 sessions), 2) Total exercise adherence (expressed as a % of maximal sessions), 3) Volume, 4) Biological sex (Male/Female), and 5) Age at baseline. This analysis will be reported (Table 6) in a secondary paper with a clear reference to the primary paper.

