## **INTRODUCTION:**

### **Aim and hypothesis**

We will conduct a randomized controlled trial (RCT) with economic evaluation investigating the clinical and cost-effectiveness of a physiotherapist-led strength exercise intervention compared to usual care as first-line treatment in patients with femoroacetabular impingement syndrome (FAIS). Furthermore, we will explore how exercise adherence and volume of a physiotherapist-led strength exercise intervention are associated with outcomes. We hypothesized that (i) 6-months of physiotherapist-led strength exercise intervention is superior (i.e.  $\geq 6$  points difference on the International Hip and Outcome Tool 33; iHOT-33), to usual care in improving hip related quality of life (QoL) in patients with FAIS after a 6 month intervention, (ii) 6-months of physiotherapist-led strength exercise intervention is cost-effective compared to usual first-line care at 12-months follow-up in patients with FAIS, and (iii) high exercise session adherence and high volume of exercise will be superior to low exercise adherence and low volume in moderating objectively- and patient-reported outcome measures in patients with FAIS.

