##### *Adherence and exercise volume*

Adherence to the exercise sessions (i.e., session adherence reported as the number of attended sessions expressed as a % of the total number of prescribed supervised and total sessions) and exercise progression, sets, repetitions, load, rate of perceived effort (RPE), duration of the exercise session, and whether the session was conducted under supervision, will be registered by the patients as they will be instructed to keep a paper-based exercise

diary. Intensity will be reported as Rating of Perceived Effort (RPE). Volume will be expressed as the product of the total number of repetitions performed and multiplied by the external load.

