aAnalyzed using linear regression. b $\beta$ , Regression coefficient. The interpretation of the crude and adjusted  $\beta$  is the change in the dependent variable for every unit of each of the independent variables. cAdjusted each of the independent variables (i.e., Adherencesupervised, AdherenceTotal, Exercise Volume, Biological Sex, Age, and Physical Activity Level). dDependent variable in each respective regression model. [95% CI]: 95% confidence interval. (p): P-value. iHOT-33: International Hip and Outcome Tool 33.

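### The adherence regression mutually adjusts three overlapping exposures and omits the baseline outcome, so its individual adjusted coefficients do not estimate each exposure's overall association with outcome and are imprecise

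*SAP*

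**What the plan says.** Hypothesis (iii), under Aim and hypothesis, is that "high exercise session adherence and high volume of exercise will be superior to low exercise adherence and low volume".

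Under Adherence and exercise volume, session adherence is "the number of attended sessions expressed as a % of the total number of prescribed supervised and total sessions", so the total measure includes the supervised sessions. On volume: "Volume will be expressed as the product of the total number of repetitions performed and multiplied by the external load".

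Under Pre-specified exploratory analyses, the dependent variable of each multiple linear regression is the change from baseline to 6 months in iHOT-33, 1 RM leg press, hop distance or one-leg rise. The predictors are given as one list: "The independent variables will be 1) Supervised exercise adherence (expressed as a % of maximal 12 sessions), 2) Total exercise adherence", followed by "3) Volume, 4) Biological sex (Male/Female), and 5) Age at baseline". The baseline value of the outcome is not among them. The section allows six predictors, from about 60 participants at 10 per variable.

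Table 6 has a crude and an adjusted column for each of the four outcomes. Footnote c describes the adjusted column as "Adjusted each of the independent variables" and names supervised adherence, total adherence, volume, sex, age and physical activity level. The wording is incomplete, but mutual adjustment is its natural meaning. Physical activity level is not in the text's list of five.

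**The concern.** A regression coefficient describes a change in one predictor with the others held still. Here the others are partly made of the same thing. Attending one more session raises total adherence, usually raises volume, and raises supervised adherence if the session was supervised. An adjusted coefficient that holds the other two fixed does not describe the patient who simply trained more, and that patient is the subject of hypothesis (iii).

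At stake is how the secondary paper reads. A real association could be split over three rows, two or all of which look null, and be reported as no association. A second problem is independent of the first: a change score is generally related to its baseline value, so an exposure that follows baseline picks up a spurious coefficient when baseline is left out.

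**Working it through.** **1. The plan's own figure.** 60 participants / 10 per variable = 6 predictors, as stated. With the 28% dropout that the sample size section allows for, 60 × 0.72 = 43.2 participants, and 43.2 / 10 = 4.3, so 4 predictors.

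**2. What the adjusted coefficients mean.** Let S be supervised and U unsupervised sessions attended, M the total prescribed, V volume. The model is

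change = b0 + bS·(S/12) + bT·((S+U)/M) + bV·V + sex + age.

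Collecting terms:
- one more unsupervised session at fixed V: bT/M;
- one more supervised session at fixed V: bS/12 + bT/M;
- the difference between the two: bS/12.

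So bS tests whether a supervised session is associated with more change than an unsupervised one at the same total attendance and volume. bT describes an extra unsupervised session with total repetitions times load unchanged. bV describes more repetitions or load at the same attendance. None is the overall association of its exposure with outcome.

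**3. Overlap.** The SAP gives neither M nor any correlation. Assumptions:
- M = 48 to 52, from the inclusion criterion of exercising twice a week for six months;
- mean attendance about 75%;
- latent correlation of supervised and unsupervised attendance 0.3 to 0.9;
- between-patient log-SD of load 0.1 to 0.5.

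Simulated results:

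| Quantity | Range |
|---|---|
| r(supervised, total) | 0.50-0.83 |
| r(total, volume) | 0.39-0.93 |
| VIF, supervised | 1.4-3.5 |
| VIF, total | 1.6-10.5 |
| VIF, volume | 1.3-8.1 |

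The standard error of total adherence is inflated by √1.6 = 1.3 to √10.5 = 3.2 times. The model is estimable, not singular.

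**4. Power for total adherence at a fixed association.** Assuming 52 sessions, latent correlation 0.3 to 0.8, load spread 30%, true standardised association 0.4 and n = 43 to 60: about 33-63% in the joint model, against 76-91% with one exposure per model.

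**5. A case where every session helps equally.** Assuming 1 iHOT-33 point per attended session, SD 19.2 (the sample size section's value), load log-SD 0.1 or 0.3, and n = 43 or 60:

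| Exposure | Mutually adjusted: rejects | Alone: rejects |
|---|---|---|
| Supervised adherence | 4-6% | 25-83% |
| Total adherence | 15-64% | 78-96% |
| Volume | 4-6% | 35-91% |

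The adjusted supervised and volume coefficients average about 0, although patients who train more do better. A joint 3-df test, which the SAP does not plan, rejects in 59-86%. Adjusted total adherence rejects in 15-26% at load log-SD 0.1 and in 34-64% at 0.3, which shows how far the answer moves with an unknown input.

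**6. Baseline omission.** Standardise volume, baseline and 6-month outcome. Let volume correlate a with baseline and have no effect of its own, and let baseline and follow-up correlate r. Regressing change on volume alone gives a coefficient of a(r − 1).
- a = 0.3, r = 0.9: 0.3 × (−0.1) = −0.03.
- a = 0.7, r = 0.5: 0.7 × (−0.5) = −0.35.

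Simulation agrees, and the coefficient returns to 0 once baseline is in the model. Both correlations are assumed. Volume contains external load, which may follow baseline strength, so the 1 RM model is the most plausible place for this.

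**7. Size of the alternative.** One exposure + baseline outcome + sex + age = 4 predictors, needing 40 participants, which 43 meets. Adding baseline to Table 6's six gives 7, above the SAP's limit of 6 even at 60 participants.

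**The case against.** Table 6 also has a crude column, which takes each exposure alone, and there total adherence keeps its power (78-96% in step 5). The adjusted model can be fitted, and total adherence retains some power in it. That stands, and it limits the harm to one of two reported columns. The crude column is not a full substitute, because it ignores sex, age and baseline: no cell of Table 6 shows one exposure adjusted for basic confounders.

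A reader might infer that the analysis cannot test hypothesis (iii) at all, or that its headline result will be misleading. The SAP supports neither. The coefficients are estimable, and nothing in the section or in Table 6 ranks the adjusted column above the crude one or attaches a decision rule to either.

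It is also fair to say that if the effect runs wholly through volume, a null for adherence at fixed volume is a correct conditional result, and the volume row should carry the effect. That case is therefore no evidence of a lost association; the equal-benefit case in step 5 is the relevant one.

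Finally, every power and bias figure rests on inputs that the SAP does not give, and 43 participants is the low end, since the dropout allowance is an upper figure. This stands too. The meaning of the coefficients in step 2 needs none of those inputs.

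**Conclusion.** The point holds in a limited form. The individual mutually adjusted coefficients do not estimate the overall association of each exposure with outcome, and they are less precise than single-exposure estimates. The first part follows from the SAP's own definitions. The size of the second depends on the assumed session total, attendance correlation, load spread and association; the direction was the same throughout the ranges tried.

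The missing baseline outcome is a separate risk of confounding, between −0.03 and −0.35 SD per SD under the assumed correlations. It is not a reason why no test exists.

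The consequence is modest: the analysis is labelled exploratory, is confined to the exercise arm and goes to a secondary paper. It does not touch the primary outcome or the economic evaluation. It does bear on one of the three numbered hypotheses, so it is worth correcting before the data are analysed.

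**What to change.** - For each of the four outcomes, replace the adjusted column's single model by three: one each for supervised adherence, total adherence and volume, every one adjusted for the baseline value of the outcome, sex and age. Reword footnote c to match.
- If the mutually adjusted model is still wanted, keep it as supplementary and label its coefficients as conditional on the other two exposures.
- Reconcile physical activity level between the text (five predictors) and Table 6 (six). If it is kept in each single-exposure model, there are 5 predictors, which by the SAP's rule need 50 participants, that is, dropout of at most 1 − 50/60 = 17%.
- The exposures remain continuous. The SAP sets no cut between high and low, so either say that hypothesis (iii) is read as a trend or define the cut in advance.

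The cost is SAP wording and a table shell, with no new data. The drawback is that more coefficients come from separate models: 3 × 4 = 12 adjusted fits instead of 4.
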